Outcome measures will be assessed at baseline, 3-, and 6-months follow-up. At the outset, we will examine the frequency distributions of all variables. Data from all PHS sites will be pooled for analysis, after confirming there is no significant heterogeneity among sites or adjusting as needed. We will compare the baseline characteristics to assess whether randomization distributed covariates evenly. We will determine whether there is differential dropout in the groups and consider developing probability-of-completion weights to obtain unbiased estimates of treatment effect. The primary analysis will assess the effects of each intervention component in terms of its association with the **primary outcome** (cotinine-confirmed or self report of cessation at 6-months follow-up), **secondary smoking outcomes** and **proximal outcomes/mediators**: (a) short vs long counseling (conditions 1/2/5/6 vs. 3/4/7/8), (b) short vs long NRT (conditions 1/3/5/7 vs conditions 2/4/6/8), and (c) provision of systematic referral or not (conditions 1-4 vs. 5-8). Given the balanced complete factorial design,⁹⁴ each of the three main effect estimates will be based on the full sample size of 640. Cross-sectional analyses will be conducted for outcomes assessed at 3, and 6 months separately. For binary outcomes, chi-square tests will be used to compare the outcomes between groups for each follow-up time. For continuous outcomes two-sample t-tests or Wilcoxon rank sum tests, whichever more appropriate, will be used to compare between groups. A longitudinal analysis using Generalized Estimating Equations (GEE) techniques will also assess the overall impact of each component by including data from all follow-up time points. The secondary analysis will examine the interaction between components, which will provide insight into whether certain combinations of components are most useful. We will test the three-way and two-way interaction terms in the regression models. If there are component interactions, we will determine whether the components are synergistic or antagonistic. Exploratory analyses will examine the moderator effects on treatment effectiveness of the intervention components and groups. Of primary interest are sociodemographic characteristics (sex, race/SES, age), smoking characteristics (quit motivation, nicotine dependence), medical history, LCS-related factors (test results, and point of study entry), delivery modality selected (phone vs. video) and language of participation (English vs. Spanish). We will test the effects of these factors in multivariable logistic regression models to determine their association with the primary and secondary smoking outcomes. We will test for interactions between intervention and these factors to determine whether

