
Sample size/ Power calculations

Power calculations are based on our primary analysis, which is to assess the effect of each intervention component (e.g., shorter counseling vs. longer counseling) on our primary outcome, 7-day point-prevalence tobacco abstinence at 6-month follow-up. This is a two-sample comparison between patients that receive one intervention component (e.g., longer counseling) and those that receive the other (e.g., shorter counseling). We conservatively estimate that 160 patients/month will have LCS, of whom 50% will be current smokers. Assuming a 50% enrollment rate, we aim to recruit a total N of 720 patients. This sample size allows us to allocate N=360 to each treatment component comparison (main effect). Our

Reference rate	Relative Risk		
	1.4	1.45	1.5
16%	0.71	0.80	0.87
17%	0.74	0.83	0.90
18%	0.77	0.86	0.92
19%	0.80	0.88	0.93
20%	0.83	0.90	0.95
21%	0.85	0.92	0.96
22%	0.87	0.93	0.97

outcome of interest will also be assessed at 3-month followup, which allows us to use a longitudinal generalized estimating equations approach wherein power is proportional to the within-person correlation. We estimate the correlation between 3 month and 6 month smoking cessation to be 0.6. Assuming N=360 patients in each condition, a Type 1 error rate of 0.05, a 25% attrition rate by 6 month follow-up, and a 15% cessation rate for the reference group, we will have 92.3% power to detect a risk ratio of 1.6 (15% vs. 21%). Under those same conditions, but with a 10% cessation rate for the reference group, we will have 79.0% power to detect a risk ratio of 1.6 (10% vs. 16%). Given that this is full factorial design, we will have the same power to detect two-way interactions between components. Further, we will also have 77.9% power to detect a risk ratio of 2.0 in the difference between our most intensive set of treatments (longer counseling, longer NRT, and community support; N=90) and our least intensive set of treatments (shorter counseling, shorter NRT, and no community support; N=90) after six months, assuming a 15% reference rate and 25% attrition.

Reduction from initial power calculations

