This study was initially powered conservatively to detect a smaller risk ratio of 1.4 and did not account for additional power provided through within-person correlation via repeated measurement of our outcome of interest. Initial power calculations, assuming a Type 1 error rate of 0.05, 25% attrition at 6 months, and no within-person correlation showed that our original N of 960 patients (N=480 per condition) gave us 85.0% power to detect a risk ratio of 1.4 with a reference rate of 15%. Updated power calculations accounting for within-person correlation of 0.6 show that this original N gives us 96.8% power to detect our target risk ratio of 1.6, assuming 25% attrition at 6 months and a 15% reference cessation rate.

Our previous power calculation assumed a 25% attrition rate at 6 months. We re-examined this assumption after halfway through the recruitment. Our new estimates are 12.7% attrition rate at 3 months and 15.9% attrition rate at 6 months. Based on these estimates, we further reduce the target recruitment from 720 to 640. Combining data from both 3-month (estimated N=559) and 6-month (estimated N=539) assessments, the effective sample size will be 768 after taking into account of within-person correlation using a conservative estimate of 0.6. The new sample size will have 70% power to detect a risk ratio of 1.6 (10% vs. 16%) and 81% power to detect a risk ratio of 1.7 (10% vs. 17%).

VII.. RISKS AND DISCOMFORTS (Stratify by common and uncommon)

Prior to enrollment, potential patients will be cautioned about the potential negative psychological and physical implications of joining the study and/or quitting smoking.

Psychological Risks

Individuals may find it stressful to answer questions and discuss their smoking behaviors. The risks associated with these discussions are minimal, especially when compared to the benefits of smoking cessation.

The potential risks to subjects include: 1) speaking with a counselor about smoking and/or cancer-related topics has the potential for increasing psychological vulnerability; 2) experiencing physical and emotional withdrawal symptoms from smoking cessation; and 3) potential side effects of using nicotine replacement therapy.

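### The only power given for N=640 (70%/81%) belongs to a pooled 3-and-6-month analysis; the plan gives none for the 6-month comparison and does not say which test decides the primary outcome

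*Combined protocol and SAP*

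**What the plan says.** All places are in Section VI of the combined protocol and SAP.

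- **Outcomes** sets the primary smoking outcome as 7-day point-prevalence abstinence at 6 months. Self-reported abstinence at 3 months is secondary.
- **Sample size/Power calculations** opens with "Power calculations are based on our primary analysis, which is to assess the effect of each intervention component", names 6-month abstinence as the outcome, and continues: "This is a two-sample comparison between patients that receive one intervention component (e.g., longer counseling) and those that receive the other". Later in the same paragraph it brings in the 3-month assessment, "which allows us to use a longitudinal generalized estimating equations approach".
- **Outcomes/analysis** says: "Cross-sectional analyses will be conducted for outcomes assessed at 3, and 6 months separately". It goes on: "For binary outcomes, chi-square tests will be used to compare the outcomes between groups for each follow-up time". It then says that GEE "techniques will also assess the overall impact of each component by including data from all follow-up time points". That sentence stands after the one that opens the primary analysis and before the one that opens the secondary analysis. Each main effect uses all 640 patients.
- **Analysis plan** counts patients lost to follow-up as smokers. A complete-data analysis is a sensitivity analysis.
- **Reduction from initial power calculations** cuts the target from 720 to 640 and says: "Combining data from both 3-month (estimated N=559) and 6-month (estimated N=539) assessments, the effective sample size will be 768", using a within-person correlation of 0.6. The result is: "The new sample size will have 70% power to detect a risk ratio of 1.6 (10% vs. 16", with 81% for 10% vs 17%.

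**The concern.** The power section announces a calculation for a two-group comparison at 6 months. At the final sample size it delivers one for a two-visit analysis. A reader who starts from its opening sentence will take 70%/81% as the chance of detecting a component effect on 6-month abstinence. If the 6-month chi-square test decides, that is too favourable, and a null main effect would tell us less than the stated power suggests.

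The larger consequence is that the decisive test is not named. The 6-month chi-square test and the GEE can disagree, and the plan has no pre-stated rule for which one answers the primary question for each of the three components. The 77.9% figure quoted after six months does not fill the gap: it concerns 90 vs 90 patients under the earlier target of 720.

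**Working it through.** **Inputs.** Total 640, equal allocation, so 320 per level of each factor. Assessed: 559 at 3 months, 539 at 6 months. Attrition 12.7% and 15.9%. Correlation 0.6. Rates 10% vs 16% and 10% vs 17%. Alpha 0.05 is stated for the larger targets and assumed unchanged at 640. Sidedness is not stated; two-sided is assumed.

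**Formula.** With n per level and p̄ = (p1+p2)/2, power = Φ{ [ |p2−p1| − 1.96·√(2p̄(1−p̄)/n) ] / √((p1(1−p1)+p2(1−p2))/n) }.

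**Step 1: reproduce the plan's figures.**
- Assessments: 559 + 539 = 1098, or 1098/640 = 1.716 per patient.
- Design effect: 1 + 0.716 × 0.6 = 1.429. Effective N: 1098/1.429 = 768, so 384 per level.
- 10% vs 16%, n = 384: (0.06 − 1.96 × 0.02427)/0.02417 = 0.514, power 69.6% (stated 70%).
- 10% vs 17%, n = 384: power 81.1% (stated 81%).
- A one-sided test at n = 384 gives 79.7%/88.5%, so the two-sided assumption is the one that fits.

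The stated figures are therefore two-visit figures.

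**Step 2: the 6-month comparison at N=640.**
- 10% vs 16%, n = 320: (0.06 − 1.96 × 0.02659)/0.02648 = 0.298, power 61.7%.
- 10% vs 17%, n = 320: power 73.7%.

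This takes 10/16/17% as rates in which missing patients already count as smokers. If they are responder rates, there are two ways to count:
- Respondents only, 539/2 = 269.5 per level: 54.4%/66.3%.
- All 640 with missing counted as smokers, so each rate is multiplied by 1 − 0.159 = 0.841 (8.41% vs 13.46% or 14.30%), n = 320: 53.4%/65.1%.

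**Step 3: put the pooled analysis on the same footing.** If responder rates are diluted at 6 months, they are diluted in the GEE too. With all 640 counted at both visits, effective N is 1280/1.6 = 800, or 400 per level. Multiplying the rates by 0.841 gives 62.9%/74.8%, about 63%/75%.

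| Reading of 10/16/17% | Pooled analysis | 6-month test | Risk ratio for 80% power, 6-month test |
|---|---|---|---|
| Missing already counted as smokers | 70%/81% (as stated) | 62%/74% | about 1.76 |
| Responder rates, diluted by attrition | about 63%/75% | 53%/65% | about 1.85 |
| Responder rates, 539 respondents only | 70%/81% (as stated) | 54%/66% | about 1.84 |

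At the stated effective N of 768, the risk ratio for 80% power is about 1.69. Under the plan's missing-as-smoker rule (first two rows), pooling accounts for 7-8 points on the first reading and about 10 on the second. The wider gap in the third row belongs to a respondents-only analysis, which the plan keeps for sensitivity.

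**The case against.** The strongest reply is that nothing is concealed. The power section introduces the GEE approach, the reduction paragraph gives both visit counts, the correlation and the effective N, and 70%/81% is never called 6-month-only power. The GEE sentence also comes before the secondary analysis is introduced, so the GEE can be read as part of the primary analysis. On that reading the stated power fits its test approximately. This stands, and it is why the shortfall can be stated only conditionally. It does not supply a 6-month figure or name the decisive test. The description as a two-sample comparison, and the word "also" in the sentence "techniques will also assess the overall impact of each component by including data from all follow-up time points", lean towards chi-square without settling it.

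Four stronger readings are tempting, and the documents do not support them:

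- *The 6-month power is simply 62%/74%.* That is the favourable end. The plan does not say which kind of rate it assumes.
- *The 6-month test misses 47%/35% of true effects against a stated 30%/19%.* This sets diluted rates against an undiluted pooled figure. Like for like, the pooled power also falls, to about 63%/75%.
- *768 is an arithmetic error*, because 1098/1.6 = 686. It follows from the average number of assessments per patient, as shown above.
- *The trial presents itself as well powered at a risk ratio of 1.6.* It states 70% there.

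**Conclusion.** The point holds as a mismatch and an omission. The power section announces a 6-month two-sample comparison, the only power at N=640 is for the pooled longitudinal analysis, and no sentence ranks the two tests.

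- **If the 6-month chi-square test decides,** its power is between about 53% and 62% for 10% vs 16%, and between about 65% and 74% for 10% vs 17%, depending on what the assumed rates mean.
- **If the GEE decides,** 70%/81% is approximately right, provided that the effect is the same at both visits. The primary result is then an average over 3 and 6 months, which the outcome definition and the opening of the power section do not say.

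Either way the text needs a change. The conclusion rests on two-sided alpha 0.05, equal allocation, and the plan's own attrition and correlation. The design itself is not in question.

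**What to change.** 1. In **Outcomes/analysis**, name the decisive test of the primary outcome: the 6-month chi-square test or the GEE. If it is the GEE, align the primary outcome under **Outcomes** and the opening of **Sample size/Power calculations** with a result averaged over 3 and 6 months.
2. In **Reduction from initial power calculations**, label 70%/81% as the power of the pooled 3-and-6-month GEE, assuming equal effects at both visits.
3. In the same paragraph, state whether 10%, 16% and 17% count missing patients as smokers or are responder rates. Add the matching 6-month power and detectable risk ratio at N=640: 62%/74% and about 1.76, or 53-54%/65-66% and about 1.84-1.85.

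The cost is a few sentences. The power shown for the 6-month outcome becomes less favourable. Enrolment, conduct and data collection do not change.

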expressed the need for time and repeated offers to engage in a cessation program. Given these barriers, it is imperative to offer cessation treatment at multiple points of LCS delivery. We propose that the LCS process provide 3 systems-based patient-engagement opportunities that 1) integrate into the screening process, 2) include primary care and radiology, and 3) use a population health management perspective.

II. SPECIFIC AIMS (Research Objectives)

Aim 1: To develop a centralized smoking cessation treatment (care coordination and intervention components) at 10 MGB LDCT-LCS screening sites.

Aim 2: To test the effectiveness of the intervention for smoking cessation in a randomized controlled trial using a factorial design to assess 3 intervention components:

- (a) Duration of counseling contact (repeated proactive sessions delivered by a trained tobacco treatment specialist using phone or videoconferencing telehealth platform);
- (b) Duration of NRT, and
- (c) Referral to community-based resources to address social barriers.

Aim 3: To evaluate the reach, adoption, implementation, and maintenance of the intervention. The components of the LCS-tailored intervention are informed by our preliminary studies and conceptual frameworks.

III. SUBJECT SELECTION

Patients: Inclusion and exclusion criteria. Patients who are scheduled to undergo LDCT-LCS at a participating PHS LCS site, speak English or Spanish, and are current smokers are eligible. Current smokers will be defined as those who have smoked a cigarette, even a puff, in the last 30 days. Smokers will fulfill the Medicare coverage requirement (age 50-80 years, 20+ pack/years). Smokers do not have to be ready to quit smoking. We will exclude patients who are: (1) undergoing lung CT as part of a diagnostic or abnormal follow-up evaluation, (2) unable to give informed consent due to psychiatric or cognitive impairment as determined in consultation with study PI or treating clinician, (3) who do not have access to a telephone or cannot communicate by telephone, or (4) do not reside within the United States of America.

IV. SUBJECT ENROLLMENT

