(3) Systematic screening for social barriers to care. If randomly assigned to receive this resource, the tobacco cessation counselor will encourage patients to address social barriers to cessation by receiving a personalized referral from a web-based tool named Aunt Bertha (<https://www.auntbertha.com/>) to systematically screen and provide local free or low cost referrals for social barriers to care. This approach was used successfully in CLIQ and was found to be significantly associated with cessation.⁵⁰ A branching logic questionnaire to evaluate social needs, suggests services near their residence or other desired location that may help them, and

then selects the referrals that meet their needs. Once services are selected, the tobacco cessation counselor can mail/encrypted email/text the selected referrals to patients.

Research staff will use a Partners approved text messaging service to contact patients whom have consented to be sent study text messages.

Treatment fidelity

Treatment fidelity will be monitored using recommendations by the Treatment Fidelity Workgroup of the NIH Behavior Change Consortium (BCC). The BCC cites monitoring 5 areas to promote reliability of behavioral interventions: Design (review tobacco counseling documentation weekly), Training (ongoing: a randomly selected 15% of session recordings will be reviewed by [name] for MI and protocol adherence), Treatment Delivery (recordings and documentation of session content), Receipt of Treatment (session review of topics covered) and Enactment of Treatment skills/knowledge (patients set treatment goals and progress).

Assessments

Baseline: At enrollment, data will be collected from the patient either on the phone by the RA or on an iPad via REDCap, as described above. Additional baseline information will be obtained from the EHR (see assessment plan below for specific data collected). Patients will be offered a \$20 incentive to complete the survey.

Outcome assessments: Patient-reported outcomes will be assessed at 3 and 6 months post-enrollment by telephone, email or mail and recorded in REDCap. Individuals will be offered a \$20 incentive to complete each outcome assessment. To minimize patient burden, the survey will be piloted and kept to approximately 10-15 minutes. Other outcome measures will be obtained from the EHR. Prior to a patient's 6 month survey, we will be sending out promotional items such as notepads, reusable bags, stress balls, and hand sanitizer.

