Organizational Readiness. Site characteristics and site readiness will be measured at each study site. Employees will undergo local training and then each attending employee will answer the readiness items, identified by the SCALE collaboration. Data will be collected anonymously, and employees will be consented through a waiver of documented informed consent. Responses to these items will be collected at baseline and at the end of the intervention phase of the study.

Research staff may also use a Partners approved text messaging service to contact patients who have agreed to be sent text messages during the consent process. This will be used to maximize outcomes from study videos, follow up surveys, and study reminders.

The Area Deprivation Index (ADI) is a measure for social economical status. We plan on using ADI to control for social and economical factors that are not otherwise reported. We plan on using census.gov to import a csv file of participant addresses which will return the 2020 census block group for those addresses. Names and study details will not be included in the process. By knowing the census block group of an address, we can then link that address to the 2020 ADI score.

VI. BIOSTATISTICAL ANALYSIS

Assessment Plan

Outcomes

Primary smoking outcome: 7-day point-prevalence tobacco abstinence at 6-month follow-up.

Secondary smoking outcomes (1) self-reported 7-day abstinence at 3-, and 6- months follow-up; (2) significant reduction (>50% decrease from baseline in cigarettes/day⁸¹); and (3) >24-hour intentional quit attempt at 3-, and 6-months follow-up.

Measures

Moderators

Sociodemographic and biological characteristics [baseline only]. *EHR*: Sex, age, primary insurance, language preference for sessions and study materials. *Survey*: Race/ethnicity, education level, employment, and religiosity. Medical history [baseline and follow-up]. *EHR*: Comorbid tobacco-related disease, ambulatory visits, alcohol consumption. Screening result. *EHR*: Lung RADS score, results of any diagnostic tests (CT or biopsy). Smoking characteristics [baseline and follow-up]. *Survey*: Current cigarettes/day, number of years smoked, e-cigarette use, past and current use of cessation medication and other tobacco products, 24-hour intentional quit attempt, nicotine dependence (2-item Heaviness of Smoking Index from the Fagerström Test for Nicotine Dependence [FTND] which have predictive validity with the overall FTND^{82, 83}).

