These risks will be described by the research assistant and will be clearly outlined in the consent script. Among enrolled patients, in the event that a patient is determined to be actively suicidal and at risk for self-harm at any of the study contact points, the study PIs will be immediately contacted and the appropriate clinical intervention effected. These procedures would be followed in the case of active suicidality or homicidality, as well as in the case of abuse, neglect or risk of harm to a minor or elder.

Toxicities and Side Effects

Nicotine Replacement Therapy (Nicotine Patch)

The transdermal nicotine patch has been an FDA-approved treatment for nicotine dependence since 1991, and in 1996, the patch was approved for over-the-counter sale. Up to 50% of patients using the nicotine patch will have a local skin reaction. Skin reactions are usually mild and self-limiting but may worsen over the course of therapy. Local treatment with hydrocortisone cream (1%) or triamcinolone cream (0.5%) and rotating patch sites may ameliorate such local reactions. In less than 5% of patients, such reactions require the discontinuation of nicotine patch treatment.

Nicotine is not an independent risk factor for acute myocardial events, but NRT should be used with caution among those in the immediate (within 2 weeks) postmyocardial infarction period, those with serious arrhythmias, and those with serious or worsening angina pectoris. Mild sleep disturbances, such as vivid dreaming or insomnia, have been reported for approximately 12% of patients wearing the transdermal nicotine patch for 24 hours.⁹⁸ Other less common side effects are nausea, dizziness, tachycardia, upset stomach, restlessness, and headaches.

As our patient population may have existing physical and psychological symptoms, we will make every effort to determine if any symptom reported has its onset concurrent with or is exacerbated by medication use. In cases of severe or intolerable symptoms, patients will be instructed to discontinue use of the study medication and to contact their physician.

VIII. POTENTIAL BENEFITS

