Safety monitoring plan: The exclusion criteria are designed to prevent patients at a high risk of medical and psychiatric complications from participating in study. However, if unexpected conditions appear to be placing patients at a higher risk than anticipated, the exclusion criteria will be amended. Any medical complications, which are considered to be related to the study, will be reported to the site PI, who will report them to the subject's treating physician. The site PI will review the progress of all study participants on an at least monthly basis. Any adverse events related to study participation will be reported to the IRB.

The main safety risks for the study include the potential for psychological discomfort with

surveys and counseling as well as side effects from study medications. In order to protect against risk from pharmacotherapy usage, these steps will be taken:

- (1) Medication is being provided only to patients who receive counseling sessions. At each call, patients are specifically asked about any side effects or problems. Study staff will be required to report any unexpected or questionable reports of adverse effects to the study PIs. These will be reviewed at the weekly study staff meeting. If more urgent, the PI will review immediately.
- (2) The study physicians (Drs. [name] and [name]) will provide back up to study staff for all medical questions that arise during participant enrollment or study progress.
- (3) The PIs will review any serious adverse events and report them appropriately to the IRB and NIH. Reports are to be submitted within 5 working days/7 calendar days of the date the investigator first becomes aware of the problem. Each will be reviewed by the PIs to ensure that the readmission is not related to study medication.

Data Sharing

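### SAEs reach the study mainly through patient contact, so the SAE summary depends on counseling attendance and assignment; a uniform EHR check would be a cheap improvement

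*Combined protocol and SAP*

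**What the plan says.** **Review and reporting.** Item (3) of the Safety monitoring plan (section IX) opens broadly: "The PIs will review any serious adverse events and report them appropriately to the IRB and NIH". Reports are due within 5 working days/7 calendar days of the investigator learning of the problem. The item closes with "Each will be reviewed by the PIs to ensure that the readmission is not related to study medication". The annual report to the NIH is to contain a summary of adverse events and SAEs.

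**Setting.** Section III: "Patients who are scheduled to undergo LDCT-LCS at a participating PHS LCS site, speak English or Spanish, and are current smokers are eligible". Counseling is by phone or video. No hospital admission forms part of eligibility or of the intervention.

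**How events come to light.** Item (1) of the Safety monitoring plan says "At each call, patients are specifically asked about any side effects or problems" and "Medication is being provided only to patients who receive counseling sessions". Staff pass unexpected or doubtful reports to the PIs for weekly review. The site PI looks at every participant's progress at least monthly; no data source is given. Under Protection of Human Subjects, staff alert the investigators to a patient who appears distressed, and patients receive the investigators' contact details at the start.

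**What is collected at follow-up.** Section V, Outcome assessments, provides for surveys at 3 and 6 months and adds: "Other outcome measures will be obtained from the EHR". The EHR medical-history items in section VI, marked for baseline and follow-up, are "Comorbid tobacco-related disease, ambulatory visits, alcohol consumption". Screening and diagnostic test results also come from the EHR. No adverse-event item appears among the listed survey measures, and no admission, emergency visit or death appears among the listed EHR items.

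**The concern.** Two things stand out. First, the only sentence on how relatedness is judged speaks of a *readmission*, an event that presupposes an earlier admission this trial does not have. It also mentions medication alone and not study procedures.

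Second, the plan describes no single method for finding SAEs that applies to everyone randomized. The only routine question about problems is tied to counseling calls. The number of calls is itself a randomized factor, and attendance varies from patient to patient. A count built this way partly measures how often people were asked. If SAEs are later set out by condition, a difference between counseling arms could reflect opportunity to report. A patient who stops taking calls because of a serious event is also one whom this system is likely to miss.

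**Working it through.** The plan states no SAE figure to reproduce. The check sets the described routes side by side and then counts the calls offered.

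**1. Routes by which a medical SAE could become known**

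| Route | Needs patient contact? | Same in all eight conditions? |
|---|---|---|
| Question at each counseling call (section IX) | Yes | No: 4 or 8 calls offered |
| Distress noticed during surveys or counseling (Protection of Human Subjects) | Yes | Not for the counseling part |
| Patient contacts the investigators (same section) | Yes | Open to all |
| Monthly progress review (section IX) | Not stated; no data source | Yes, as written |
| 3- and 6-month survey measures (section VI) | Yes | Same schedule, but no SAE item listed |
| Follow-up EHR items (sections V and VI) | No | Yes, but no admission, emergency visit or death listed |

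The EHR extract is the one listed source that is both uniform and independent of contact, and it has no field for these events.

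**2. Calls offered, by factor**

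Inputs: 640 patients and eight equal conditions (section VI), so 640 / 8 = 80 per condition; 4 or 8 sessions (section V); condition numbering from section VI, Outcomes/analysis.

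- Short counseling (conditions 1, 2, 5, 6): 4 × 80 = 320 patients; 320 × 4 = 1,280 calls offered.
- Long counseling (conditions 3, 4, 7, 8): 320 × 8 = 2,560 calls offered. Ratio 2,560 / 1,280 = 2.
- Short NRT (conditions 1, 3, 5, 7): (4 + 8 + 4 + 8) / 4 = 6 calls per patient.
- Long NRT (conditions 2, 4, 6, 8): (4 + 8 + 4 + 8) / 4 = 6 calls per patient.
- Conditions 1–4 and conditions 5–8 (the referral factor): (4 + 4 + 8 + 8) / 4 = 6 in each.

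The imbalance lies wholly on the counseling factor. The NRT and referral contrasts are balanced on calls offered.

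**3. Consequence for a count**

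Let *r* be the true SAE risk, equal in both counseling arms, and let *c₄* and *c₈* be the chances that an SAE becomes known with 4 or 8 calls offered. Expected recorded SAEs are 320 × *r* × *c₄* and 320 × *r* × *c₈*, so their ratio is *c₈* / *c₄*. This equals 1 only if the extra four calls add nothing to capture. The documents give no call timing, attendance or SAE rate, so the ratio cannot be estimated. The 2:1 figure describes opportunities offered and is not a bias in recorded events.

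**The case against.** The strongest reply is that the plan does more than wait for complaints. Patients are asked directly at every call, staff must pass reports on, review is weekly, and patients can reach the investigators. That stands. A reader might infer that SAEs surface only if a patient happens to mention them; the active question at calls contradicts this.

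Next, the wording fault is small. Item (3) opens by covering any SAE, so first admissions and deaths are already within review and reporting. That also stands. A reader might conclude that the causality step leaves such events out, but *each* refers back to all SAEs and one noun is wrong. Taken alone, the sentence needs only an editorial correction.

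Third, item (3) belongs to steps meant to guard against medication risk. Calls offered are equal across the NRT arms, patients given NRT are by rule in counseling contact, and no between-arm safety test is planned, only a summary. This narrows the point: no stated analysis is biased, and the NRT contrast is not affected through calls offered. It does not remove the point, because the summary itself still depends on attendance and counseling assignment.

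Finally, the documents do not show that the EHR would reveal every admission or death. That is a fair limit on the remedy. A partial source applied equally to all conditions still adds something the contact-based routes lack.

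**Conclusion.** The point holds as a worthwhile, low-cost improvement. As described, medical SAEs become known mainly through patient contact. The opportunity to be asked differs 2:1 by randomized counseling arm, and no listed survey or EHR item picks up admissions, emergency visits or deaths. Patients who cannot be reached are the most likely to be missed. This rests on the lists in sections V and VI being the full collection plan and on the monthly review having no unstated EHR source.

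Four stronger readings are tempting and are not supported:

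- *About 101 patients (640 − 539) have no route for an SAE to surface.* That figure counts expected 6-month survey non-completers. The listed survey measures include no SAE item, so completing the survey is not the safety route. Non-completers may still take calls or contact the investigators.
- *A given number of admissions would be missed.* The documents contain no admission rate, so any such count would rest on an outside assumption.
- *A named cardiac risk would go undetected.* Section VII says "NRT should be used with caution among those in the immediate (within 2 weeks) postmyocardial infarction period", which is a caution about use. The same sentence says nicotine is not an independent risk factor for acute myocardial events.
- *Deaths cannot be told apart from loss to follow-up.* The Analysis plan classes patients lost to follow-up as current smokers and is silent on how deaths are recorded. Silence justifies asking for a rule; it does not show that the two are merged.

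**What to change.** 1. Add hospital admissions, emergency visits and deaths, with dates and primary reason, to the EHR extract already planned at follow-up. Cover every randomized patient from enrollment to 6 months and use the same schedule in all eight conditions, for example at the 3- and 6-month points.
2. Report SAEs by condition from that source, and flag deaths separately from loss to follow-up.
3. In section IX, Safety monitoring plan, item (3), replace the closing sentence with an assessment by the PIs of whether each serious adverse event is related to study medication or study procedures. This removes *readmission* and leaves the answer open.
4. Keep the questions at calls. The extract supplements them.

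**Cost.** A few more fields in an extract already planned, using medical record numbers the study already holds, and one reworded sentence. There will be some chart-review time and PI time for causality assessment. Events treated outside the health system will not be seen, and the extract is retrospective, so it cannot replace prompt reporting from calls.
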